|  Autologous patella tendon |  Hamstring tendons |  Quadriceps tendon |
|  Other _____ | | |

Previous Graft Harvest:

- | | | |
|--|--|--|
|  Autologous patella tendon |  Hamstring tendons |  Quadriceps tendon |
|--|--|--|

Document drill hole placement for ligament reconstruction on these figures.

- Post-operative data collection will include both subjective and objective outcomes measures.
 - Subjective outcomes of donor site morbidity will include VAS for ADL's, VAS for kneeling, IKDC subjective knee evaluation form, and a return to sports/subjective performance questionnaire. Each post operative office visit will require approximately 10 minutes of patient time to fill out the subjective questionnaires.
 - Collected at 14days and 1,3,6,12,18 and 24 months

Example of how a VAS questionnaire is converted to numerical data points:

[figure not shown]

Figure 1. A, a VAS for recording the severity of pain. The question posed would read, “How bad is the pain at its worst?” B, the patient places a mark at what he feels is the appropriate point on the line. C, through simple measurement techniques, this graphic representation may be converted to a numerical value.

Visual Analog Scale

Activities of Daily Living

For each question, place a mark on the line between the two descriptions which you think describes your knee relative to the two extremes.

No Knee Discomfort
With Activities of Daily

Constant Knee Pain
With Activities of Daily

Visual Analog Scale

Kneeling Pain

For each question, place a mark on the line between the two descriptions which you think describes your knee relative to the two extremes.

No Knee Discomfort
With Kneeling

Unable to Kneel
Due to Knee Pain

IKDC Subjective Knee Evaluation Form

2000 IKDC SUBJECTIVE KNEE EVALUATION FORM

Your Full Name _____

Today's Date: ____/____/____
Day Month Year

Date of Injury: ____/____/____
Day Month Year

SYMPTOMS*:

*Grade symptoms at the highest activity level at which you think you could function without significant symptoms, even if you are not actually performing activities at this level.

1. What is the highest level of activity that you can perform without significant knee pain?

- 4 Very strenuous activities like jumping or pivoting as in basketball or soccer

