We plan to enroll approximately 100 patients with 50-treatment/50 controls. Power analysis was based upon previous studies examining kneeling pain using a VAS in patients undergoing ACL reconstruction with Autologous Bone Patellar Tendon Bone graft harvest. Feller et al (2001) reported kneeling pain to be 4.5+/-2.1 4 mo. after surgery, Wipfler et al (2011) reported kneeling pain to be 1.6+/-0.7 1 yr after surgery, and Siebold et al (2006) reported kneeling pain to be 4.0+/-3.1 3.8 yr after surgery (mean +/-SD reported). A 2-point difference in kneeling pain between groups would be regarded as clinically significant. The between subject SD for kneeling pain of averaged 2.0 for the 3 studies cited above with an upper limit of approximately 3.0. Therefore we conservatively based the sample size estimate to demonstrate a 2.0 difference in VAS pain between groups on a SD of 3.0. It is estimated that with 35 patients per group there will be 80% power to detect a 20% difference in kneeling pain (2 points on a 10 point scale) at an alpha level of 0.05. This estimate was calculated using the equation described by Kirkwood et al (1988).

Assuming a loss to follow up of up to 30% at two years, adequate sample recruitment was determined to be 50 per group or 100 total.

References Cited for Power Analysis

- 4:Kirkwood BR (1988). Calculation of required sample size. In *Essentials of Medical Statistics.* pp 191-200. Oxford. Blackwell Scientific Publications.

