The secondary outcome measures are objective and include radiographic evidence of graft site healing and clinical objective measurements. The primary and secondary outcomes measures for the two groups will be statistically analyzed to evaluate for any differences between the two groups over time using mixed model analysis of variance with Group (PRP vs. no PRP) and the between subjects factor and Time (14d, 1,3,6,12,18 and 24 months post op) as the within subjects factor. Bonferroni corrections will be used for between group or between time pair-wise planned comparisons.

The de-identified data will be entered into an Excel spreadsheet and maintained on a password-protected computer. Once data collection is complete, the principal investigator (SJN) and/or his research assistant (MM) will destroy the master hard copy of identifier codes. Confidentiality of data, data integrity, review of data and study quality will be monitored by the principal investigator and/or his research assistant. Baseline data, demographic data, primary and secondary outcomes will be analyzed using summary statistics, standard deviations and 95% confidence intervals for quantitative data. Qualitative data will be assessed using frequencies and percentages.

J. Informed Consent:

Informed valid written consent will be obtained from all patients at the time of enrollment. This will be in accordance to IRB consent forms

K. Potential Risks & Discomforts:

- a. *Platelet Rich Plasma:* Since PRP is a formulation created entirely from the participants own blood, the complications and risks are extremely low. The anesthesiologist who prepares the blood is highly skilled and will carefully sterilize the skin prior to obtaining the sample. Another side effect that is common is an initial increase in pain and inflammation at the site where the PRP is injected. This occurs because the platelets and blood sample contain natural chemicals that stimulate the immune system. This type of complication is short lived and when it does occur, is treated effectively with pain medication and anti-inflammatory medications, such as Ibuprofen. PRP is not recommended for individuals who have a known bleeding disorder (bleed easily) or are on a medication known to thin the blood such as Coumadin or Lovenox. This makes sense because these patients are more likely to bleed than an individual who has normal bleeding characteristics.

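### The 80% power in section I is for one uncorrected kneeling-VAS comparison at an unnamed visit; the plan tests seven visits with Bonferroni correction and does not say which test decides the trial.

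*Combined protocol and SAP*

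**What the plan says.** All of this is in section I (Statistical Analysis/Data Management) unless noted.

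- **Power.** The plan claims that "with 35 patients per group there will be 80% power to detect a 20% difference in kneeling pain", meaning 2 points on a 10-point scale, at an alpha of 0.05. On the SD it says: "The between subject SD for kneeling pain of averaged 2.0 for the 3 studies cited above with an upper limit of approximately 3.0". It then adds: "Therefore we conservatively based the sample size estimate to demonstrate a 2.0 difference in VAS pain between groups on a SD of 3.0". Enrolment of 50 per group allows for up to 30% loss at two years. Neither the visit nor the sidedness of the test is given.
- **Analysis.** The model is a mixed model analysis of variance with Group between subjects, "and Time (14d, 1,3,6,12,18 and 24 months post op) as the within subjects factor". Then: "Bonferroni corrections will be used for between group or between time pair-wise planned comparisons". No comparison is exempted, and no number of comparisons is given.
- **Outcomes.** "The primary and secondary outcomes measures for the two groups will be statistically analyzed", but the primary outcome is never named. "The secondary outcome measures are objective and include radiographic evidence of graft site healing", together with clinical objective measurements. Section F lists the subjective outcomes as VAS for ADLs, "VAS for kneeling, IKDC subjective knee evaluation form, and a return to sports/subjective performance questionnaire".

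**The concern.** The power statement and the analysis describe different tests. The first is one comparison of two means at the full 0.05. The second offers a Group effect, a Group by Time effect and seven visit-specific group differences, the last at a reduced alpha. The plan does not say which of these decides whether PRP worked, so a reader cannot attach the 80% to the deciding test.

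Two things are at stake. If corrected visit tests decide, each has less power than stated under the plan's own assumptions. And because the candidate tests respond to different patterns of effect over time, the same data could be read as a success or a failure under a rule chosen after the results are known. Kneeling VAS is presumably primary, since it is the only outcome powered, but that is an inference.

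**Working it through.** **Inputs from section I:** difference 2.0; SD 3.0 (cited average 2.0); alpha 0.05; 35 evaluable and 50 enrolled per group; seven visits.

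**Assumptions:** two-sided test; Bonferroni family size k; for tests that use all visits, equal correlation ρ between visits and no missing data.

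**Step 1. Reproduce the plan's figure.**
- Standard error = 3.0 × √(2/35) = 0.717. Noncentrality = 2.0/0.717 = 2.789.
- Normal approximation: Φ(2.789 − 1.960) = Φ(0.829) = 79.6%. Noncentral t with 68 degrees of freedom: 78.5%.
- Sample size: 2 × [3.0 × (1.960 + 0.842)/2.0]² = 35.3 per group. Enrolment: 35/(1 − 0.30) = 50.
- A one-sided test would need only 28 per group, so the plan evidently used a two-sided one.

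The stated 80% is therefore one uncorrected two-group test.

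**Step 2. Apply Bonferroni.** Use the same noncentral t calculation with two-sided alpha 0.05/k. At 50 per group the standard error is 0.600 and the noncentrality 3.333. At 35 per group and SD 2.0 the noncentrality is 2.0/[2.0 × √(2/35)] = 4.183.

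| k | alpha per test | 35/group, SD 3.0 | 50/group, SD 3.0 | 35/group, SD 2.0 |
|---|---|---|---|---|
| 1 | 0.0500 | 78.5% | 91.0% | 98.5% |
| 2 | 0.0250 | 69.0% | 85.3% | 96.9% |
| 3 | 0.0167 | 63.2% | 81.3% | 95.6% |
| 7 | 0.0071 | 51.0% | 72.0% | 91.6% |

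At 35 per group, power per test returns to 80% once the SD falls to about 2.66 (k = 2), 2.53 (k = 3) or 2.31 (k = 7).

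**Step 3. Other tests the plan could mean** (35 per group, SD 3.0, ρ from 0.3 to 0.9).
- *Group main effect, uncorrected.* The SD of a patient's seven-visit mean is 3.0 × √[(1 + 6ρ)/7], which is 1.90 at ρ = 0.3 and 2.87 at ρ = 0.9. If the 2-point difference holds at all visits, power is 99% and 82% respectively. If it holds at one visit only, the averaged difference is 2/7 = 0.29 and power is about 7% to 9.5%.
- *Group by Time.* Noncentrality = (35/2) × Σ(dⱼ − d̄)²/[9(1 − ρ)], where dⱼ is the group difference at visit j and d̄ the mean of the seven. A constant difference makes the sum zero, so power equals alpha, about 5%. For a difference at one visit only, Σ = 4 × (1 − 1/7) = 3.43, and power is about 61% at ρ = 0.3, rising to nearly 100% at ρ = 0.9.
- *Significance at any of seven corrected visits* (simulation, 40,000 trials per case). Power is about 94% (ρ = 0.3) down to 68% (ρ = 0.9) if the difference holds throughout, and 52% to 53% if it exists at 24 months only.

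**The case against.** **The shortfall uses the least favourable planning values.** SD 3.0 is the plan's cautious choice, and 35 per group is what remains after the full two-year loss. Earlier visits should have more patients. This stands as a limit on size: with everyone retained, families of two and three stay above 80%, and at SD 2.0 even seven visits do. But SD 3.0 with 35 per group is the basis on which the plan claims 80%, and the deciding test is unnamed at any SD.

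**A reader might infer that 80% power is unattainable except with one uncorrected visit.** The documents do not support that. Under a sustained difference the Group main effect has 82% to 99%. The any-corrected-visit rule also reaches 80% over much of the correlation range. With an assumed gradual loss from 50 to 35 per group, its power under a sustained difference is 84% to 98%. The 51% is per visit, not the trial's chance of success. What stands is that the plan adopts none of these rules.

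**A reader might also infer an inflated false-positive rate.** If success on any of the main effect, Group by Time or a corrected visit counted, the chance under no effect would be about 10% to 11% for kneeling VAS. But the plan states no such rule. Most of that figure is simply two tests at 0.05 each (1 − 0.95² = 9.75% if independent), and Bonferroni already guards against picking a favourable visit. It illustrates the ambiguity and does not measure this plan's error rate.

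**Kneeling VAS may not be the only primary outcome.** Calling the secondary measures objective fits equally well with all the subjective outcomes being primary. That is a fair reading, and a further reason to declare the primary outcome.

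**Conclusion.** The point holds. The stated 80% belongs to one uncorrected comparison at one visit; section I plans Bonferroni-corrected comparisons across seven visits and identifies neither the deciding test nor the family size. On the plan's SD of 3.0 and 35 per group, power per corrected test falls from about 79% to 69%, 63% or 51% for families of two, three or seven.

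These figures assume a two-sided test and a family size the plan does not give. They apply per test, and they shrink or vanish with better retention or a lower SD. The gap in specification depends on none of these assumptions. It should be fixed, but it does not show that the sample size is wrong: 35 evaluable per group is adequate if a single-visit contrast at 0.05 is made primary.

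**What to change.** Amend section I before unblinding, and preferably before the half-accrual interim analysis in section L:

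1. Declare kneeling VAS the primary outcome.
2. Name one Group contrast from the mixed model as the primary test, at two-sided 0.05 without Bonferroni. It can be one visit of the sponsor's choosing or the average over visits.
3. Keep the stated 80% only if a single visit is chosen. For any other deciding rule, restate the power with its assumed SD, between-visit correlation and pattern of effect over time. If corrected visit tests are to decide, give both per-visit and any-visit power.
4. Make all other visits and measures secondary, with Bonferroni and a stated number of comparisons per family.
5. Revise the sentence describing the secondary measures as objective so that it also covers VAS for ADLs, the IKDC subjective form and return to sports.

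The cost is wording; no extra patients are needed. The trade-off is real, though. A single primary visit can miss an effect at other times: if the difference existed only at the first three visits, a 24-month test would be significant about 5% of the time. An average over visits dilutes a short-lived effect: with the difference at three of seven visits, the averaged difference is 6/7 = 0.86 and power is about 23% to 46%. The sponsor should choose according to when benefit is expected, and accept that a restated power may be less favourable.

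### The Group-by-Time ANOVA over seven visits has no sphericity correction, covariance structure or stated error term, so the interaction test, and possibly the visit comparisons, may not hold 5%

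*Combined protocol and SAP*

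**What the plan says.** Section I (Statistical Analysis/Data Management) analyses primary and secondary outcomes with a "mixed model analysis of variance with Group (PRP vs. no PRP) and the between subjects factor and Time" as the within-subjects factor. Time has seven levels: 14 days and 1, 3, 6, 12, 18 and 24 months. Planned pairwise comparisons, between groups or between times, are Bonferroni-corrected. The section gives no covariance structure, sphericity test or correction, or degrees-of-freedom method. It does not say which variance enters the group comparison at each visit, and no other section supplies this.

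The sample-size paragraph of the same section cites three earlier studies. The first "reported kneeling pain to be 4.5+/-2.1 4 mo. after surgery", the second "reported kneeling pain to be 1.6+/-0.7 1 yr after surgery" and the third "reported kneeling pain to be 4.0+/-3.1 3.8 yr after surgery". From these the sponsor "conservatively based the sample size estimate to demonstrate a 2.0 difference in VAS pain between groups on a SD of 3.0". That single planning SD is not tied to a visit.

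**The concern.** The between/within wording is that of a split-plot repeated-measures ANOVA. Its Time and Group-by-Time F tests are exact only under sphericity, meaning that the differences between any two visits all have the same variance. Two features of this trial make that doubtful.

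- The visits are unevenly spaced. Scores at 14 days and 1 month are likely to correlate more strongly than scores at 14 days and 24 months.
- Kneeling pain is measured on a bounded scale during recovery, so its spread may change as the mean moves. In the cited studies the smallest SD (0.7) goes with the smallest mean (1.6).

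The stated question is whether the groups differ over time. The Group-by-Time test and the visit comparisons answer it, and these are the results exposed. Bonferroni adjusts for the number of tests; it does not repair a wrong standard error or wrong degrees of freedom.

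**Working it through.** **1. The plan's own figure.** Inputs from section I: difference 2.0, SD 3.0, alpha 0.05 (taken as two-sided), power 80%.

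n = 2 × [3.0 × (1.96 + 0.84) / 2.0]² = 35.3 per group. The plan's 35 is reproduced (36 if rounded up), and 35 / 0.70 = 50 enrolled per group. This is a two-sample calculation with no repeated-measures covariance in it, so the present point does not change it.

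**2. Set-up of the check.** Null simulation, 35 per group, seven visits, complete data, 20,000 replicates per scenario. The documents give no correlations, so two are assumed: constant at 0.5, and AR(1) at 0.7 between successive visits. The AR(1) form follows visit order, not calendar time.

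**3. Group-by-Time test.** F = MS(Group-by-Time) / MS(error), referred to 6 and 6 × 68 = 408 degrees of freedom. Without sphericity, both should be multiplied by ε = tr(M)² / [6 tr(M²)], where M is the covariance matrix of six orthonormal visit contrasts. With equal SDs and AR(1) 0.7, ε = 0.58, so about 3.5 and 237 degrees of freedom are appropriate. Using 6 and 408 gives a rejection rate of 8.2%; Greenhouse-Geisser brings it to 4.9%. With equal SDs and constant correlation, ε = 1 and the uncorrected rate is 5.1%.

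**4. Visit comparisons, if one variance is pooled.** The pooled variance is the mean of the seven visit variances. At a visit with SD s, the approximate error of a nominal 5% test is 2 × [1 − Φ(1.96 × pooled SD / s)].

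- SDs rising evenly from 0.7 to 3.1: mean variance 29.75 / 7 = 4.25, pooled SD 2.06. At s = 3.1: 1.96 × 2.06 / 3.1 = 1.30, error 19%. At s = 0.7: 5.77, error about 0%.
- Only the two SDs inside the trial window (2.1 through 6 months, then 0.7): (4 × 4.41 + 3 × 0.49) / 7 = 2.73, pooled SD 1.65. At s = 2.1: 1.54, error 12%. At s = 0.7: about 0%.

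**5. Results over assumed SD patterns.** Family error is for seven visit comparisons, each at 0.05/7; where two values are shown they are for constant and AR(1) correlation.

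| Visit SDs (assumed) | Per-visit error, highest / lowest SD | Bonferroni family error | Group-by-Time, constant 0.5 | Group-by-Time, AR(1) 0.7 |
|---|---|---|---|---|
| Equal, 3.0 | 5% / 5% | 4.0%, 3.9% | 5.1% | 8.2% |
| 0.7 rising to 3.1 | 19% / 0% | 11.6%, 10.7% | 7.3% | 9.7% |
| 2.1 to 6 months, 0.7 at 12, then 3.1 | 14% / 0% | 8.4%, 8.0% | 6.5% | 8.7% |
| 2.1 to 6 months, then 0.7 | 12% / 0% | 10.9%, 10.0% | 7.1% | 8.9% |
| 3.0 falling to 1.5 | 13% / 0.3% | 7.0%, 6.5% | 5.9% | 8.6% |
| 3.0 falling to 2.0 | 10% / 1.4% | 5.4%, 4.9% | 5.2% | 8.5% |
| 2.5 falling to 2.0 | 8% / 3% | between 4% and 5% | 5.3% | 8.4% |

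**6. After correction.** Greenhouse-Geisser gives a Group-by-Time error of 4.3-5.0%. In the first six patterns, testing each visit on its own variance gives a per-visit error of 4.6-5.4% and a family error of 3.7-4.2%. The Group main effect stays at 4.5-5.3% in those patterns with no correction.

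**The case against.** The strongest reply is that the plan never says one variance is pooled. A planned group comparison at a visit can be an ordinary two-sample test on that visit's data, and then its error rate is correct. This stands. A reader might infer that the plan commits to pooled visit comparisons with wrong error rates, but the text is silent on the error term, so the 0-19% range is conditional.

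A reader might also infer that the protocol's own SDs disprove equal variances. They do not. The three values come from three studies, so differences between studies cannot be separated from differences over time. The third study is titled as one in females, and its SD of 3.1 was measured at 3.8 years, beyond the 24-month visit. The SDs make unequal spread plausible, no more.

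A third tempting inference is that pooling leaves the low-variance visits without power. At the protocol's own target ("A 2-point difference in kneeling pain between groups would be regarded as clinically significant") this is false. With SDs falling from 3.0 to 1.5, the pooled SD is 2.30 and the rejection threshold is 1.96 × 2.30 × √(2/35) = 1.08. The true standard error at the SD-1.5 visit is 1.5 × √(2/35) = 0.36. The unadjusted power is Φ[(2 − 1.08) / 0.36], about 99.5%, and about 91% after Bonferroni for seven visits.

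It is also fair that Bonferroni keeps the family error at or below about 5% when the spread is mild. None of this answers the Group-by-Time result, which needs only decaying correlation and no assumption about SDs or pooled contrasts.

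**Conclusion.** The point holds as an uncorrected test and an omission. Run in its ordinary form, the planned Group-by-Time test has a type I error of about 8% under AR(1) 0.7 with equal SDs, and about 7-10% over most of the unequal-SD patterns tried. It is closer to 5% when correlation is constant and the spread is small. Inflation of the visit comparisons needs two further conditions: a pooled error term, and visit SDs that differ. With both, unadjusted per-visit error could run from about 0% to 19%. Bonferroni family error could be about 7-12% with a marked spread, about 5% for SDs of 3.0 to 2.0, and below 5% for 2.5 to 2.0.

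All sizes rest on assumed correlations and SD patterns, complete data and 35 per group. The Group main effect and the sample size are not affected. This should be corrected before analysis, because it otherwise leaves to the analyst a choice that changes the error rates.

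**What to change.** In section I, specify a linear mixed model with Group, categorical Time and Group-by-Time, an unstructured covariance across the seven visits and Kenward-Roger degrees of freedom. Test the group difference at each visit on its own standard error, with Bonferroni as planned.

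If the ANOVA is preferred, keep it, but require Greenhouse-Geisser for Time and Group-by-Time and visit-specific variances for the planned group comparisons. Either version is valid whether or not the variances differ, so the sponsor need not accept any particular SD pattern.

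The cost is a sentence or two of text and no new patients, visits or data. The unstructured model estimates more covariance parameters (7 × 8 / 2 = 28), which is reasonable with about 70 to 100 patients.

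### Bonferroni for the planned pair-wise comparisons is valid, but Holm's step-down rule gives the same family-wise protection, never rejects less, and costs one sentence

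*Combined protocol and SAP*

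**What the plan says.** Section I (Statistical Analysis/Data Management) plans a mixed-model analysis of variance with treatment group as the between-subjects factor and "Time (14d, 1,3,6,12,18 and 24 months post op) as the within subjects factor". For the comparisons that follow it says: "Bonferroni corrections will be used for between group or between time pair-wise planned comparisons". It mentions no step-down procedure. It does not say how many comparisons form a family, or whether between-group and between-time comparisons share one.

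The sample-size text in the same section takes the larger of the SDs it considers: "Therefore we conservatively based the sample size estimate to demonstrate a 2.0 difference in VAS pain between groups on a SD of 3.0". It concludes that "with 35 patients per group there will be 80% power" for that difference, "at an alpha level of 0.05". Planned enrolment is "approximately 100 patients with 50-treatment/50 controls", which allows for up to 30% loss at two years. Section I also promises 95% confidence intervals for quantitative data and does not describe them as adjusted or simultaneous.

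**The concern.** Single-step Bonferroni holds every comparison to the same strict threshold, even after other comparisons in the family have been declared significant. Holm relaxes the threshold after each rejection and still protects the family-wise error at the same level, whatever the dependence between the tests. For accept-or-reject decisions Holm is therefore never worse and sometimes better.

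The pair-wise comparisons are how the trial would say at which visits the PRP and control groups differ. A true effect at some visit could be reported as not significant under Bonferroni when Holm, on the same data and with the same error protection, would have detected it. The question is how often that would happen with this trial's own figures.

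**Working it through.** **Inputs from section I.** Difference 2.0 points, SD 3.0, 35 evaluable per arm, alpha 0.05, seven visits.

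**Assumptions, because the plan is silent.** Two-sided testing; a family of the seven between-group comparisons of one outcome at 5% family-wise; the same n and SD at every visit; equal correlation between visits of 0.3 to 0.7.

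**Step 1: the plan's own sample size.** n per arm = 2 × (1.960 + 0.842)² × 3.0² / 2.0² = 35.3, against the stated 35. A one-sided test would need 28, so two-sided is the reading that fits. Allowing for loss: 35 / (1 − 0.30) = 50 per arm, as stated.

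**Step 2: power of one unadjusted comparison.** SE = 3.0 × √(2/35) = 0.717. Effect/SE = 2.0 / 0.717 = 2.789. Power = Φ(2.789 − 1.960) = 79.6%, which reproduces the stated 80%.

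**Step 3: the same comparison under Bonferroni.** The threshold is 0.05/7 = 0.0071, with critical value 2.690. Power = Φ(2.789 − 2.690) = 53.9%.

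**Step 4: Holm.** Order the seven p-values. Compare the smallest with 0.05/7 = 0.0071, the next with 0.05/6 = 0.0083, then 0.05/5 = 0.0100, and so on up to 0.05, stopping at the first failure. The first step is the Bonferroni test, so the chance of at least one rejection is identical under the two rules. Later thresholds are only looser, so no Bonferroni rejection is lost.

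**Step 5: simulation.** Seven correlated z statistics, 200,000 trials per scenario, 2-point effect at the affected visits, 35 per arm:

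| Visits truly affected | Bonferroni, power per affected visit | Holm, power per affected visit |
|---|---|---|
| 1 of 7 | 54% | 54% |
| 3 of 7 | 54% | about 56% |
| 4 of 7 | 54% | about 58% |
| 7 of 7 | 54% | 64-65% |

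With all seven affected, the chance of detecting all seven rises from 8-24% to 31-49%. In no simulated trial did Holm miss a visit that Bonferroni rejected. In runs with correlations of 0, 0.5 and 0.8, simulated family-wise error was at most 4.9% for both rules.

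**Step 6: sensitivity.**
- With 50 per arm and correlation 0 to 0.8, Bonferroni gives 74%. Holm gives 74%, 76-77% and 82-87% with one, three and seven visits affected.
- With a 1-point effect at all seven visits and 35 per arm, the figures are about 10% for Bonferroni and 11-12% for Holm (correlation 0.3 to 0.7).

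**The case against.** The strongest reply is that the plan contains no error here. Bonferroni is prespecified, controls the family-wise error and contradicts nothing else in the document. That stands, and it limits the point to an optional improvement.

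The size of the gain is also open to challenge. The largest figures need a constant 2-point benefit at all seven visits, and the plan gives reason to doubt that. One of the studies cited in section I reports mean kneeling pain of 1.6 at one year; from that control mean a 2-point reduction is impossible at 12 months. The other two cited means, 4.5 and 4.0, would allow it. Section K calls an early increase in pain and inflammation after PRP common, which argues against a full benefit at 14 days. So the rows with fewer affected visits, where the gain is 0 to about 4 percentage points, deserve at least as much weight.

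Thirty-five per arm is the count expected at two years. Earlier visits may have up to 50, where Bonferroni already gives 74%.

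A reader might infer that Bonferroni gives power away for nothing. The documents do not support that. Nothing is lost when only one visit is affected, nor in the chance of finding any visit. Bonferroni also has simple matching simultaneous intervals, which Holm lacks. That last advantage counts for little here, because the plan promises only ordinary 95% intervals.

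A simpler change, rewording the sentence to cover only the between-group visit comparisons, would do harm. It would remove the existing correction for between-time comparisons, of which there could be 7 × 6 / 2 = 21 per outcome.

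**Conclusion.** The point holds as a cheap improvement to a valid plan. Under the assumed family, moving from Bonferroni to Holm adds nothing to power at an affected visit if one visit is affected, about 2 percentage points if three, about 4 if four, and 10 to 11 if all seven. This rests on 35 per arm, SD 3.0, a 2-point effect and correlation 0.3 to 0.7. The family of seven and its 5% level are inferences: alpha 0.05 appears only with the sample size, and section I states no family size.

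A reader might also infer that Holm would bring the visit comparisons back to the planned 80%. At 35 per arm it does not in any scenario examined; the highest figure is about 65%. The 80% belongs to one unadjusted comparison, and changing the correction rule does not alter that.

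**What to change.** Reword the sentence in section I along these lines: *Holm step-down corrections (family-wise two-sided alpha 0.05) will be used for the planned pair-wise comparisons, applied separately for each outcome to the seven between-group visit comparisons and to the between-time comparisons.*

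This keeps the between-time protection and states the families and the alpha, which the current text leaves open. The seven-visit family applies to outcomes collected at all seven visits, such as the two VAS scores and the IKDC forms in Appendices B and C. The 3-month X-ray and the 6-month MRI are read once and have no such family.

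The cost is one sentence, with no extra patients, visits or data. If simultaneous intervals matching the tests are wanted later, they will be less simple than Bonferroni intervals; the ordinary 95% intervals now promised are unaffected.
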